9.2.3.1.2 Method of Detecting Adverse Events and Serious Adverse Events

Care will be taken not to introduce bias when detecting adverse events and/or serious adverse events. Open-ended and non-leading verbal questioning of the subject is the preferred method to inquire about adverse event occurrence.

9.2.3.1.3 Follow-up of Adverse Events and Serious Adverse Events

After the initial adverse event/serious adverse event report, the investigator is required to proactively follow each subject at subsequent visits/contacts. All adverse events and serious adverse events will be followed until resolution, stabilization, until the event is otherwise explained, or the subject is lost to follow-up (as defined in Section 8.3). Further information on follow-up procedures is given in Section 12.4.

All new information for previously reported serious adverse events must be sent to Amgen within 24 hours following knowledge of the new information. If specifically requested, the investigator may need to provide additional follow up information, such as discharge summaries, medical records, or extracts from the medical records. Information provided about the serious adverse event must be consistent with that recorded on the Event CRF.

9.2.3.1.4 Regulatory Reporting Requirements for Serious Adverse Events If subject is permanently withdrawn from protocol-required therapies because of a serious adverse event, this information must be submitted to Amgen.

Prompt notification by the investigator to the sponsor of serious adverse events is essential so that legal obligations and ethical responsibilities towards the safety of subjects and the safety of a study treatment under clinical investigation are met.

The sponsor has a legal responsibility to notify both the local regulatory authority and other regulatory agencies about the safety of a study treatment under clinical investigation. The sponsor will comply with country-specific regulatory requirements relating to safety reporting to the regulatory authority, IRBs/IECs, and investigators.

Individual safety reports must be prepared for suspected unexpected serious adverse reactions according to local regulatory requirements and sponsor policy and forwarded to investigators as necessary.

An investigator who receives an individual safety report describing a serious adverse event or other specific safety information (eg, summary or listing of serious adverse events) from the sponsor will file it along with the Investigator's Brochure and will notify the IRB/IEC, if appropriate according to local requirements.

To comply with worldwide reporting regulations for serious adverse events, the treatment assignment of subjects who develop serious, unexpected, and related adverse events may be unblinded by Amgen before submission to regulatory authorities. Aggregate analyses may also be unblinded by the Safety Assessment Team as appropriate.

Investigators will receive notification of related serious adverse events reports sent to regulatory authorities in accordance with local requirements.

9.2.3.2 Pregnancy and Lactation

Details of all pregnancies and/or lactation in female subjects and, if indicated, female partners of male subjects will be collected after the start of study treatment and until 5 months after receiving study drug.

If a pregnancy is reported, the investigator is to inform Amgen within 24 hours of learning of the pregnancy and/or lactation and is to follow the procedures outlined in Section 12.5. Amgen Global Patient Safety will follow-up with the investigator regarding additional information that may be requested.

Abnormal pregnancy outcomes (eg, spontaneous abortion, fetal death, stillbirth, congenital anomalies, ectopic pregnancy) are considered serious adverse events.

Further details regarding pregnancy and lactation are provided in Section 12.5

9.2.3.3 Vital Signs

The following measurements must be performed: systolic/diastolic blood pressure, heart rate, respiratory rate, and temperature. Subject must be in a supine position in a rested and calm state for at least 5 minutes before blood pressure assessments are conducted. If the subject is unable to be in the supine position, the subject should be in most recumbent position as possible. The position selected for a subject should be the same that is used throughout the study and documented on the vital sign CRF. The temperature location selected for a subject should be the same that is used throughout the vital signs CRF. Record all measurements on the vital signs CRF.

9.2.3.4 Electrocardiograms (ECGs)

Subject must be in supine position in a rested and calm state for at least 5 minutes before ECG assessment is conducted. If the subject is unable to be in the supine position, the subject should be in most recumbent position as possible. ECGs should be performed in a standardized method, in triplicate, and run consecutively (ie, < 30 seconds apart), prior to blood draws or other invasive procedures. Each ECG must include the following measurements: QRS, QT, QTc, RR, and PR intervals.

- Single ECG at Screening (cohorts 1-6) and at all time points for cohort 7 only
- ≥ 3 baseline ECGs collected ≥ 30 minutes apart, with each baseline ECG in triplicate run consecutively (ie, < 30 seconds apart) [ie, total ≥ 9 ECGs] (cohorts 1-6)
- Triplicate ECGs at time points after dosing (cohorts 1-6)

Baseline is defined as day 1 pre-dose for all cohorts. The PI or designated site physician will review all ECGs. ECGs will be transferred electronically to an ECG central reader for analysis per Amgen instructions. Once signed, the original ECG tracing will be retained with the subject's source documents. At the request of the sponsor, a copy of the original ECG will be made available to Amgen. Standard ECG machines should be used for all study-related ECG requirements.

9.2.3.5 Vital Status

This section is not applicable.

9.2.3.6 Suicidal Risk Monitoring

Liraglutide is considered to be a central nervous system (CNS)-active study treatment. In addition, there have been some reports of suicidal ideation and behavior when it has been given to some subjects with obesity. The sponsor considers it important to monitor for such events before and during this clinical study.

It is unknown whether AMG 598 may be associated with an increased risk of suicidal ideation or behavior.

Subjects being treated with AMG 598 and/or liraglutide must be monitored appropriately and observed closely for suicidal ideation and behavior or any other unusual changes in behavior. Consideration is to be given to discontinuing AMG 598 and/or liraglutide in subjects who experience signs of suicidal ideation or behavior.

Families and caregivers of subjects being treated with AMG 598 and/or liraglutide are to be instructed to monitor subjects for the emergence of unusual changes in behavior, as well as the emergence of suicidal ideation and behavior, and to report such symptoms immediately to the study investigator.

Baseline assessment of suicidal ideation and behavior and treatment-emergent suicidal ideation and behavior will be assessed during the study using C-SSRS and Patient Health Questionnaire 9 (PHQ-9). Refer to Section 12.9 and 12.10 for more information.

9.2.4 Clinical Laboratory Assessments

Refer to Section 12.2 for the list of clinical laboratory tests to be performed and to the Schedule of Activities (Section 2.2) for the timing and frequency.

The investigator is responsible for reviewing laboratory test results and recording any clinically relevant changes occurring during the study in the Event CRF. The investigator must determine whether an abnormal value in an individual study subject represents a clinically significant change from the subject's baseline values. In general, abnormal

laboratory findings without clinical significance (based on the investigator's judgment) are not to be recorded as adverse events. However, laboratory value changes that require treatment or adjustment in current therapy are considered adverse events. Where applicable, clinical sequelae (not the laboratory abnormality) are to be recorded as the adverse event.

All protocol-required laboratory assessments, as defined in Section 12.2, must be conducted in accordance with the laboratory manual and the Schedule of Activities (see Section 2.2).

Laboratory/analyte results that could unblind the study will not be reported to investigative sites or other blinded personnel until the study has been unblinded.

9.2.4.1 Pregnancy Testing

A high sensitive (urine or serum) pregnancy test should be completed at screening and within 7 days of initiation of investigational product for females of childbearing potential.

Note: Females who have undergone a bilateral tubal ligation/occlusion should have pregnancy testing per protocol requirements. (If a female subject, or the partner of a male subject, becomes pregnant it must be reported on the Pregnancy Notification Worksheet, see (Figure 12-2). Refer to Section 12.5 for contraceptive requirements. Additional pregnancy testing should be performed at monthly intervals during treatment with protocol-required therapies and 30 days +/- 3days after discontinuing protocol-required therapies.

Additional on-treatment pregnancy testing may be performed at the investigator's discretion or as required per local laws and regulations.

9.2.5 Biomarker Assessments

Longitudinal effects on lipid levels (eg, total cholesterol, low density lipoprotein cholesterol [LDL-C], high density lipoprotein cholesterol [HDL-C], and triglycerides) and potential effects on glycemic control (HbA1c) and bone metabolism (CTX and P1NP) will be assessed as detailed in the Schedule of Activities.

9.2.6 Pharmacokinetic Assessments

All subjects enrolled into the study will have pharmacokinetic samples assessed. Whole blood samples of approximately 5 mL will be collected for each measurement of serum concentrations of AMG 598 and plasma concentration of liraglutide as specified in the Schedule of Activities (Section 2.2). Instructions for the collection and handling of

biological samples will be provided by the sponsor. The actual date and time (24-hour clock time) of each sample will be recorded.

Drug concentration information that may unblind the study will not be reported to investigative sites or blinded personnel until the study has been unblinded.

9.2.7 Pharmacodynamic Assessments

Venous blood samples of approximately 5 to 7.5 mL will be collected for measurement of AMG 598 treatment PD effects at each time point specified in the Schedule of Activities. Concentration-time profiles and AUCs for metabolic parameters (glucose, insulin, c-peptide, GIP, GLP-1, glucagon, and FFAs) will be assessed.

9.2.8 Pharmacogenetic Assessments

If the subject consents to the optional pharmacogenetic portion of this study, DNA analyses may be performed. These optional pharmacogenetic analyses focus on inherited genetic variations to evaluate their possible correlation to the disease and/or responsiveness to the therapies used in this study. The goals of the optional studies include the use of genetic markers to help in the investigation of obesity and/or to identify subjects who may have positive or negative response to AMG 598. Additional samples are collected for this part of the study. For subjects who consent to this/these analysis/analyses, DNA may be extracted from residual cell pellets retained from the first plasma PD blood draws.

The final disposition of samples will be described in Section 12.6.

9.2.9 Antibody Testing Procedures

Blood samples for antibody testing are to be collected as outlined in the Schedule of Activities (Section 2.2). Bioanalytical testing for anti-AMG 598 antibodies will be conducted on these samples. Subjects who test positive at the final scheduled study visit, defined as the end of study (EOS) visit, and have clinical sequelae that are considered potentially related to an anti-AMG 598 antibody response will be asked to return for additional follow-up testing. Sample collection and testing will occur approximately every 3 months from EOS until: (1) the antibody response is negative or (2) the subject has been followed for a period of at least 1 year (± 4 weeks) post administration of AMG 598. All follow up results, both positive and negative will be communicated to the sites. More frequent testing or testing for a longer period of time may be requested in the event of safety-related concerns. Follow-up testing will not be required where it is established that the subject did not receive AMG 598.

9.2.10 Biomarker Development

Biomarkers are objectively measured and evaluated indicators of normal biologic processes, pathogenic processes, or pharmacologic responses to a therapeutic intervention.

Biomarker development can be useful in developing markers to identify disease subtypes, guide therapy, and/or predict disease severity.

Amgen may attempt to develop test(s) designed to identify subjects most likely to respond positively or negatively to AMG 598, to investigate the mechanism of action of AMG 598 and/ or further the biological understanding of obesity and related metabolic disorders.

Blood samples (approximately 11 mL per collection) are to be collected for biomarker development at the time points specified in the Schedule of Activities (Section 2.2).

9.2.11 Health Economics

Medical resource utilization and health economics data, associated with medical encounters, may be collected in the CRF by the investigator and study-site personnel for all subjects throughout the study. Protocol-mandated procedures, tests, and encounters are excluded.

The data collected may be used to conduct exploratory economic analyses and will include:

- Number and duration of medical care encounters, including surgeries, and other selected procedures (inpatient and outpatient)
- Duration of hospitalization (total days or length of stay, including duration by wards)
- Number and type of diagnostic and therapeutic tests and procedures
- Outpatient medical encounters and treatments (including physician or emergency room visits, tests and procedures, and medications).

9.2.12 Optional Substudies

The pharmacogenetic testing is optional in this study.

Obtain confirmation that the pharmacogenetic and future testing portions of the Informed Consent Form has been signed prior to performing optional substudy procedures.

9.2.13 Other Assessments

Dual-energy x-ray absorptiometry (DXA) scans will be conducted as outlined in the Schedule of Activities (Section 2.2). DXA scans for bone density measurements of the

spine and hip/femur will be performed in cohorts 1-6. DXA scans of body composition measurements will be performed in cohort 7.

10. Statistical Considerations

10.1 Sample Size Determination

The sample size for the study is based on practical considerations. For safety considerations, with up to 66 subjects receiving AMG 598 (6 subjects in each of cohorts 1-6 and 30 subjects in cohort 7), there is a 96.6% chance of detecting an adverse event with a true incidence rate of 5% or greater and a 99.9% chance of detecting an adverse event with a true incidence rate of 10%.

In cohort 7, with a sample size of 30 subjects per group, there is approximately an 80% probability of observing a mean treatment difference in percent change from baseline in body weight between AMG 598 and placebo of > 3%, assuming a true treatment difference of 5%. This assumes a standard deviation for percent change from baseline in body weight of 7% in each treatment group.

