All adverse events and use of concomitant medication will be collected for the duration of the study, up to and including the EOS visit. All treatment-emergent AEs or laboratory abnormalities will be followed until either: a) resolution of the abnormality, b) it is considered stable in the opinion of the Principal Investigator, or c) subject is lost to follow up.

For a full list of study procedures, including the timing of each procedure, please refer to Section 9.2 and the Schedule of Activities in Table 2-1 to Table 2-3.

Statistical Considerations

Descriptive statistics will be provided for selected demographics, safety, PK and PD data. Data for subjects receiving placebo will be combined across the monotherapy cohorts and across the combination therapy cohorts.

Descriptive statistics on continuous measurements will include means, medians, 25th and 75th percentiles, standard deviations, and ranges, while categorical data will be summarized using frequency counts and percentages. PK, PD and clinical laboratory data will be summarized at each time point when samples are collected.

The number and percentage of subjects reporting any treatment-emergent adverse events will be tabulated by system organ class and preferred term and will be further classified by relationship to treatment. SAEs and clinically significant changes in clinical laboratory test values, ECG, or vital signs will be noted. Both exploratory graphical and model-based PK/PD analyses may be conducted with selected PD markers.

The sample size for the study is based on practical considerations. For safety considerations, with up to 66 subjects receiving AMG 598, there is a 96.6% chance of detecting an adverse event with a true incidence rate of 5% or greater and a 99.9% chance of detecting an adverse event with a true incidence rate of 10%.

Cohort 7 with 30:30 randomization will allow for 80% probability of observing a mean treatment difference in percent change from baseline in body weight between AMG 598 and placebo of > 3%, assuming a true treatment difference of 5%

For a full description of statistical analysis methods, please refer to Section 10.

Sponsor Name: Amgen, Inc.

2. Study Schema and Schedule of Activities

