3.1 Study Rationale

Obesity is a growing global health crisis that is in critical need of safe and effective therapies. Currently approved products provide modest weight loss from baseline with issues of discontinuation due to the side effects of nausea and GI intolerability, as well as lack of continued efficacy. The current study evaluates the safety and tolerability, PK, and PD of multiple ascending doses of AMG 598 alone, and in combination with liraglutide, as a potential weight loss therapy for subjects with obesity. AMG 598, a human monoclonal antibody, binds the glucose dependent insulinotropic polypeptide receptor (GIPR), and blocks the binding of its endogenous ligand (glucose-dependent insulinotropic polypeptide [GIP]) preventing activation of the receptor and downstream pathways. Nonclinical animal studies demonstrated that GIPR antagonism resulted in significant (5-8%) weight loss compared to vehicle control. When combined with commercially available glucagon-like peptide-1 (GLP-1) receptor agonists, AMG 598 lead to a > 20% weight reduction in overweight and obese animals. Thus, in addition to evaluating AMG 598 safety and tolerability, PK and PD alone or in combination with liraglutide (a GLP-1 receptor agonist), the current study also examines the safety and preliminary weight loss efficacy of AMG 598 in a cohort of subjects who have been maintained on a stable dose of liraglutide. The sample size for this specific cohort (30:30 subjects in cohort 7) is based on practical considerations and statistical analysis for the detection of meaningful weight loss. The rationale for dose selection was based on PK and safety analysis of preliminary data collected in the first-in-human (FIH) single ascending dose study of AMG 598 in subjects with obesity. The blinded safety data from the AMG 598 FIH study suggests single doses of AMG 598 have been generally well tolerated up to 560 mg SC, with no serious adverse events (SAE), deaths, or withdrawals related to adverse events reported.

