5.2.1 Replacement of Subjects

Subjects who withdraw from the study or who discontinue study drug administration prematurely may be replaced at the discretion of Amgen in consultation with the investigator. The replacement subject will be assigned to receive the identical treatment as the replaced subject.

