10.2.4 Handling of Missing and Incomplete Data

The frequency of missing and incomplete data is expected to be low in this study and therefore, missing data will not be imputed. Methods for handling incomplete dates will be covered in the Statistical Analysis Plan.

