9.7.2.3 Whole Body Composition by DXA

Summary of absolute and percent change from baseline values in body composition, including measures of total bone mineral context (BMC), total fat mass, total lean mass and visceral adipose tissue (VAT), as measured by whole body DXA will be summarized for subjects in cohort 7.

9.7.2.4 Weight, Waist Circumference and BMI:

Summary of absolute and percent change from baseline values in body weight, weight circumference and BMI will be summarized.

Mean percent change from baseline in weight by visit for all treatment groups will also be graphed.

10. Changes From Protocol-specified Analyses

There are no changes to the protocol-specified analyses.

11. Literature Citations / References

Amgen. AMG 598 Investigator's Brochure, Edition 1.

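### Cohort 7 sample size: the stated inputs give an 86.6% chance of an observed weight difference above 3%, not about 80%

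*Protocol*

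**What the plan says.** Protocol 10.1 supports the size of cohort 7 with one weight-loss calculation. It begins "In cohort 7, with a sample size of 30 subjects per group" and claims "approximately an 80% probability of observing a mean treatment difference in percent change from baseline in body weight" of more than 3% between AMG 598 and placebo when the true difference is 5%. It then gives the variability: "This assumes a standard deviation for percent change from baseline in body weight of 7% in each treatment group". SAP 3.2 repeats the statement with the same inputs.

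The synopsis (Statistical Considerations) has a shorter form: "Cohort 7 with 30:30 randomization will allow for 80% probability of observing a mean treatment difference" above 3% for a true difference of 5%. It omits both the word approximately and the SD.

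Protocol 3.1 says that the sample size of this cohort "is based on practical considerations and statistical analysis for the detection of meaningful weight loss". The 80% statement is the only calculation about weight loss in either document. None of the three statements gives an alpha level, a sidedness, a test or an allowance for dropout.

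**The concern.** The statement defines its event completely: group size, SD, true difference and threshold are all given, so the probability can be computed directly. The result is not close to 80%. Either the number or its description is therefore wrong, and the mismatch appears in three places.

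The two possible repairs differ in kind. A chance of observing more than 3% is a descriptive property of the estimate. The power of a hypothesis test implies that a test will be done. A reader who recognises 80% as a conventional power figure may expect an inference on weight that the SAP does not contain. SAP 9.5 marks efficacy analyses as not applicable, and SAP 9.7.2.4 plans summaries of absolute and percent change plus a plot: "Mean percent change from baseline in weight by visit for all treatment groups will also be graphed".

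The figure is also the stated statistical justification for 60 of about 108 subjects, alongside practical grounds and the adverse-event calculation on 66 subjects.

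**Working it through.** **Inputs** (Protocol 10.1 and SAP 3.2): n = 30 per group; SD = 7% in each group; true difference δ = 5%; threshold for the observed difference c = 3%; stated probability about 80%.

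**Other figures in the same section.** With 66 subjects on AMG 598, 1 − 0.95^66 = 0.966 and 1 − 0.90^66 = 0.999. Both adverse-event figures reproduce as printed.

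**Attempt to reproduce the 80%, as described.**

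- SE = SD × √(2/n) = 7 × √(2/30) = 1.807
- P(observed difference > 3) = Φ((δ − c)/SE) = Φ((5 − 3)/1.807) = Φ(1.107) = **0.866**
- A t reference with 58 degrees of freedom gives 0.863, and a simulation of 400,000 trials gives 0.865.

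The gap is 86.6 − 80 = 6.6 percentage points.

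**What would give 80%, changing one input at a time** (0.8416 is the 80th percentile of the standard normal):

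| Input changed | Calculation | Value needed | Value stated |
|---|---|---|---|
| Threshold | 5 − 0.8416 × 1.807 | 3.48% | 3% |
| True difference | 3 + 0.8416 × 1.807 | 4.52% | 5% |
| SD | (2/0.8416)/√(2/30) | 9.2% | 7% |
| Evaluable n per group | 2 × (7 × 0.8416/2)² | 17.35 | 30 |

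**Attrition.** Using Φ(2/(7√(2/n))) with fewer evaluable subjects:

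| Evaluable per group | Probability |
|---|---|
| 30 | 86.6% |
| 27 | 85.3% |
| 24 | 83.9% |
| 21 (30% loss) | 82.3% |
| 18 | 80.4% |
| 17 | 79.8% |

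Reaching 80% needs a loss of 1 − 17.35/30, about 42%.

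**The nearest standard quantity.** Power of a two-sided 5% test of no difference at δ = 5%:

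- Normal approximation: Φ(5/1.807 − 1.960) = Φ(0.806) = 79.0%
- Noncentral t, 58 degrees of freedom: 77.6%

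This test is significant only when the observed difference exceeds 1.960 × 1.807 = 3.54% (normal) or 2.0017 × 1.807 = 3.62% (t). The 3% threshold plays no part in it. A one-sided test against a margin of 3% is far from 80%: 29.5% at alpha 0.05 and 19.7% at alpha 0.025.

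**Side figure.** With no true difference, P(observed difference > 3) = 1 − Φ(3/1.807) = 4.8%.

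**The case against.** The strongest reply is that nothing depends on the number. Protocol 10.1 opens by resting the study's size on practical grounds, body weight is an exploratory endpoint, no escalation, stopping or success rule uses 3%, and on the literal reading the error makes the design look weaker than it is. All of that stands, and it is why the point is minor.

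A second reply is that two of the three statements say approximately, and that an unstated allowance for dropout could bring 86.6% down towards 80%. Replacement is discretionary, so 30 evaluable per group is not guaranteed. This does not rescue the figure. The text computes on 30 per group and states no dropout allowance. Protocol 10.2.4 says "The frequency of missing and incomplete data is expected to be low in this study", and Protocol 5.2.1 provides that "Subjects who withdraw from the study or who discontinue study drug administration prematurely may be replaced". A loss of about 42% is hard to square with those two statements, and even a 30% loss leaves 82.3%.

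A third reply is that the wording is clear and only the number is off, so reading it as test power is speculation. It is fair that the test-power origin is an inference: no test or alpha is stated. The mismatch does not depend on that inference.

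Finally, a synopsis may abbreviate, and this one refers to Section 10 for the full methods. The missing SD there is a convenience for the reader, not an error in itself.

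**Conclusion.** The concern holds. For the event as described, the probability is 86.6%, against a stated value of about 80%: 6.6 percentage points too low, in the conservative direction. If test power was intended, the figure is near the right value (79.0% normal, 77.6% t), but the description is wrong because the 3% threshold does not belong to that calculation. Which was intended cannot be settled from the documents.

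The calculation assumes approximately normal group means, an SD of exactly 7% in both groups, and 30 evaluable subjects per group. No stated attrition, SD or threshold explains the gap. Severity is minor: no enrolment number, analysis or safety conclusion changes.

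**What to change.** Correct the synopsis, Protocol 10.1 and SAP 3.2 together, using one of two statements:

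- **(a) If the chance of an observed difference was meant:** give about 87% as the probability that the observed mean difference exceeds 3%, for a true difference of 5%, SD 7% and 30 per group. This fits the descriptive analysis in SAP 9.7.2.4.
- **(b) Only if the sponsor confirms that test power was meant:** give about 78% power for a two-sided test at alpha 0.05, with a true difference of 5% and SD 7%, and remove the 3% threshold. Because the SAP plans no test of weight, the text should say that the figure is for orientation only.

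State the SD in the synopsis so that the figure can be checked there. Optionally, add that an observed difference above 3% would occur about 5% of the time with no true difference.

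The cost is wording in three places, two of them in the protocol. It can wait for the next planned protocol amendment and SAP version and does not justify an amendment of its own. Sample size and analyses are unchanged.
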